31. Research Involving American Indian/Native Populations.....	19
32. Transnational Research	20
33. Drugs or Devices.....	20
34. Principal Investigator's Assurance	20
35. CHECKLIST SECTION.....	22
36. Partial Waiver of Consent for Screening/Recruitment	22
37. Partial Waiver of HIPAA Authorization for Screening/Recruitment	22
38. Waiver of Documentation of Consent	22
39. Alteration of Consent	Error! Bookmark not defined.
40. Full Waiver of Consent/Parental Permission.....	23

PROTOCOL TITLE: Evaluating the Effect of an Evidence-Based One Page with
Supplemental Visual Aids on the Knowledge and Perceptions of Blood Pressure
Management Among Adults with Hypertension

41.	Full Waiver of Consent/Parental Permission (Public Benefit or Service Programs)	23
42.	Full Waiver of HIPAA Authorization (Checklist).....	23
43.	Other Waiver Types (Checklist)	23
44.	Vulnerable Populations (Checklist)	23
45.	Medical Devices (Checklist).....	23
46.	Export Control (Checklist).....	23
47.	Data Transfer/Sharing (Checklist)	23
48.	Specimen Transfer/Sharing (Checklist).....	24

PROTOCOL TITLE: Evaluating the Effect of an Evidence-Based One Page with
Supplemental Visual Aids on the Knowledge and Perceptions of Blood Pressure
Management Among Adults with Hypertension

1. Objectives

1.1 To evaluate changes in patient knowledge of blood pressure management and perceptions of making lifestyle changes to manage their blood pressure after implementation of an evidence-based one-page teaching protocol with supplemental handouts and optional use of suggested apps and web sites.

1.2 The working hypothesis is that patients will improve their knowledge of blood pressure management and have more positive perceptions of making evidence-based lifestyle changes to manage their blood pressure after receiving education from PharmD students using a one-page teaching protocol with supplemental visual aids and optional use of suggested apps and web sites.

2. Background

2.1 Hypertension (HTN) affects as many as one in three adults in the United States (US); of those approximately 50 percent are managing their blood pressure in accordance with national guideline goals (Rodriguez, Friedberg, DiGovanni, Want, Whilie-Rosett, Hyound, & Natarajan, 2019). There are many comorbid conditions that come with HTN such as end-stage kidney disease, stroke, or heart attack (Rodriguez et al., 2019). Not only does living with untreated HTN lead to associated comorbid conditions that decrease the quality of life, but it also contributes to an astronomical cost the health care system to manage additional disease burden. Annual costs related to hypertension health care dollars has been reported as high as \$55.9 billion (Benjamin et al., 2019).

2.2 There has been confusion among health care providers over optimal blood pressure management due to discordance in national guidelines. The Joint National Committee 7 guideline (JNC7) recommended treatment of high blood pressure regardless of age if blood pressure was greater than 140/90 (Lenfant, Chobanian, Jones, & Roccella, 2003). JNC8 was considered to have “relaxed” the guidelines on early detection which would affect initiating treatment for people (not initiating treatment until systolic was over 150 if over age 60) (Armstrong, 2014). The ACC/AHA/AAPA/ABC/ACPM/AGA/AphA/ASH/ASPC/NMA/PCNA Guideline helps reconcile this variance between the two standards while providing a very extensive road map on how to manage adults with HTN in all aspects of care (Whelton et al., 2018).

There have been strides made to decrease disparities in treatment for ethnic minorities, however, there remains a 33 percent higher death rate for non-Hispanic blacks (NHB) for non-Hispanic blacks (NHB) for cardiovascular disease in the U.S. (Balfour, Rodriguez, & Ferdinand, 2015). This is addressed in the 2017 ACC/AHA

PROTOCOL TITLE: Evaluating the Effect of an Evidence-Based One Page with
Supplemental Visual Aids on the Knowledge and Perceptions of Blood Pressure
Management Among Adults with Hypertension

Guideline with specific guidelines on appropriate treatment and management of hypertension for minority populations (Whelton et al., 2018). New Mexico is a diverse and unique minority-majority state, making it necessary for clinicians/students to understand key treatment differences based on ethnicity. The 2017 ACC/AHA guideline also recommends HTN management to be provided in a collaborative manner (Whelton et al., 2018). The Million Hearts Initiative is a method adopted by many schools and facilities in the US (Gawlik & Melnyk, 2015) with the goal to prevent 1 million heart attacks and strokes by 2017. While 2017 has come and gone, this project is still being used to set the stage for population-driven health care accomplished through a collaborative team of health care providers (Gawlik & Melnyk, 2015). The Centers for Disease Control (CDC) and Prevention recognize the value of the role of the pharmacist improving blood pressures in the community from a population health perspective. With the ever increasing aging population, the CDC created a comprehensive resource guide for pharmacists to use in order to improve blood pressure management in communities (Di Palo & Kish, 2018). There is strong published evidence/data that supports the critical role pharmacist play to improve hypertension management which includes: medication management, patient-centered counseling, and disease state education (Di Palo, & Kish, 2018). A well-established understanding in research is from the time of findings to implementation of findings there can be a span of 15 years or greater before the general medical community implements the most recent evidenced-based guidelines (White, Dudley-Brown, & Terhaar, 2016). This study will add to the body of existing knowledge on how well patients with hypertension understand the new blood pressure goal which is lower than previous guidelines. In other words, is the medical community translating evidence three years out from the most recent guideline update in 2017 well or not?

2.3 A problem for blood pressure management specific to New Mexico is the lack primary care and specialty to identify and manage HTN. Many clinics are not accepting new patients due to provider shortages (Abundis, 2019). New Mexico is a poor state with over 50 percent of the population on some form of government assistance (Domrzalski, 2014). Those in a lower socio economic status (SES) may have difficulty with access to care, transportation to appointments, or paying for their medications. Additional research is needed on modes of improving blood pressure management in the setting of these provider shortages and health disparities.

Pharmacists are ideally positioned in the community as part of the care team by reinforcing patient-centered teaching on hypertension education. An example used in pharmacies are telephonic follow-ups or telehealth (text reminders for prescription pick up as an example) (Di Palo & Kish, 2018).

Shared decision making (SDM) is recommended in one of the latest clinical guidelines to improve adherence to recommendations made by the clinician in order to improve patient's agreement to follow through on given recommendations during

PROTOCOL TITLE: Evaluating the Effect of an Evidence-Based One Page with Supplemental Visual Aids on the Knowledge and Perceptions of Blood Pressure Management Among Adults with Hypertension

the encounter (Langford et al., 2019). The recognition of cultural differences in preferences for treatment is imperative in order to improve the disparity in care, and thereby improve blood pressure numbers for all adults in the US regardless of their ethnicity. Using the model of SDM has shown benefit for patient compliance (Langford et al., 2019).

Using the latest blood pressure guidelines set forth by the 2017 ACC/AHA recommendations (Whelton et al., 2018), and the Million Hearts Initiative guidelines (Gawlik & Melnyk, 2015) a comprehensive “one-page” with supplemental visual aids will be used. The one-page will be in the format of a single page, double sided handout that covers: medications to avoid that can increase blood pressure, and self-monitoring with the American Heart Association visual aide of how to take blood pressure on the front side. The back-side will have information on: diet, smoking cessation, and physical activity. The diet section will have a visual aid from the National Heart, Lung, and Blood Institute specific to the DASH diet recommended from the 2017 ACC/AHA guideline (Whelton et al., 2018). The smoking cessation will be addressed with the National 1-800-Quit-Now number with the participant encouraged to have a separate appointment with their PCP should this be a primary focus for them. For the purpose of this study, smoking cessation assistance requires more allocated time than what is planned for each participant. The exercise section will have a visual aid from the American Heart Association about proper type of exercise and length of time to exercise. There will be a table provided for quick reference with evidenced based recommended websites and apps for the participant should they have access to the internet. These handouts are included with this submission. The one-page document is included with the submission as “My Planned Behavior for Managing my Blood Pressure.”

3. Study Design

3.1. Study design: prospective clinical trial with human participants assigned to an intervention of a one-page handout with supplemental visual aids and optional use of suggested apps and websites as an educational intervention to improve their knowledge of blood pressure management through behavior changes recommended to them.

3.2. N/A. There will be no blinding in this study.

4. Inclusion and Exclusion Criteria

4.1. Patients will be screened with an initial interview which will be conducted over the phone. The interview script is included in this submission as “UNM HTN Phone Screen for Potential Participants.” Their Walgreens medication profile will also be reviewed to verify that they are on medications for hypertension.

PROTOCOL TITLE: Evaluating the Effect of an Evidence-Based One Page with
Supplemental Visual Aids on the Knowledge and Perceptions of Blood Pressure
Management Among Adults with Hypertension

- 4.2.** The inclusion criteria will be: adults from 18 to 75 years old, ability to self-consent, English-speaking, able to read/write English, currently prescribed at least one medication for treatment of essential primary hypertension.
- 4.3.** There will be no special populations in this study. This study will not include adults unable to consent; individuals who are not yet adults (infants, children, teenagers); pregnant women; or prisoners.
- 4.4.** Pregnant women will be excluded due to the complexity of hypertension in pregnancy, which warrants management by an OB/GYN or other specialists. Potential participants will be asked if they are pregnant or planning to become pregnant using the screening document “UNM HTN phone screen for potential patients.” Children are excluded for three reasons: 1) the writer is only certified as an NP to work with adults; 2) the focus of this study is the population at greatest risk for high blood pressure which is adults; and 3) children with high blood pressure are rarely diagnosed with essential primary hypertension, and should be managed by a specialist. We do not have the resources to provide adequate materials in Spanish or other languages commonly spoken in NM, and further research may be needed on the effect of the intervention for non-English speaking patients.

5. Number of Subjects

- 5.1.** This is a single site study and will be done at one location, Walgreens Store #6587 in Albuquerque, New Mexico. There will be 50 participants recruited.
- 5.2.** The number to be recruited will be 50.
- 5.3.** Based on statistical analysis from UNM Statistics Department, a sample size of at least 45 patients is needed. The number to be recruited at the onset will be 50 to account for attrition.

6. Study Timelines

- 6.1.**
 - Duration of individual’s participation in research: The total expected duration of participants’ active participation is less than 60 minutes. The participants will have mailed to them at the start of the study: one-page with supplemental handouts/visual aids, list of suggested apps and web sites, pre/post survey and pre/post-test with self-addressed stamped envelopes (SASE) to return their information, and a pill box.
 - Recruitment for this study will begin August-September 2020. Duration anticipated to enroll all subjects: 30 days
 - Total duration for researchers to complete the study: Recruitment will occur through end of Sept 2020; additional follow-up phone calls will occur through

PROTOCOL TITLE: Evaluating the Effect of an Evidence-Based One Page with
Supplemental Visual Aids on the Knowledge and Perceptions of Blood Pressure
Management Among Adults with Hypertension

September-November 2020. Data analysis will occur during the month of December 2020. Manuscript preparation and submission to scholarly publications will occur shortly thereafter with the target of January 2021.

7. Study Endpoints

- 7.1.** Primary endpoint: change in participant's knowledge of blood pressure management; change in participant's perception of making lifestyle changes to manage their hypertension
- 7.2.** Describe any primary or secondary safety endpoints: N/A
- 7.3.** Describe any exploratory endpoints:
 - 1: Participants will be asked to rate the usefulness, ease of reading, and attractiveness/visual appeal of each handout they were provided.
 - 2: Participants who choose to use any apps or web sites will be asked for feedback on usefulness, ease of reading/access, and attractiveness/visual appeal for each app or web site used.
 - 3: The subset of participants who choose to use electronic resources will be compared to the subset of participants who do not to compare any differences in the primary outcome.

8. Research Setting

- 8.1.** Site or location: Walgreens Store #6587 in Albuquerque, NM.
- 8.2.** We will recruit potential subjects from Walgreens Store #6587 in Albuquerque, NM. Participants will be recruited over the phone.
- 8.3.** Research will be performed from Walgreens Store #6587 in Albuquerque, NM.
- 8.4.** Describe the composition and involvement of any community advisory board: N/A
- 8.5.** This is a partnership with UNM College of Pharmacy, Walgreens Pharmacy, and a Doctor of Nursing (DNP) student enrolled in the DNP program at Missouri State University (MSU). Per MSU policy, once the IRB is submitted and approved through UNM, the IRB approval from UNM with a summary paragraph will be submitted to MSU for record. [name], DNP candidate, will be responsible for submitting the approved UNM IRB with summary paragraph to the MSU IRB board to complete this requirement. A cede letter is included in this submission.

9. Resources Available

- 9.1.** The PI is [name], PharmD with UNM College of Pharmacy, who has completed a two-year fellowship in Cardiovascular Pharmacotherapy and holds a Certificate in Clinical & Translational Research.

PROTOCOL TITLE: Evaluating the Effect of an Evidence-Based One Page with Supplemental Visual Aids on the Knowledge and Perceptions of Blood Pressure Management Among Adults with Hypertension

[name], MSN, ANP-C (certification for adult care) is completing this project as part of a DNP program at MSU. She will be responsible for diagnosing, managing care, ordering labs/diagnostics, and referrals to specialty care. She has completed board certification by the American Nurse Association for Cardiovascular Nursing.

[name] PharmD: will act as preceptor and liaison between UNM College of Pharmacy and Walgreens Pharmacy. [name] has extensive experience providing care in the community pharmacy setting.

PharmD students who have an understanding they will participate in this study from the start/end of the study will work under the supervision of [name]. The students will be in the clinical rotation of their studies as P4 PharmD students.

- 9.2.** [name] MSN, ANP-C will be responsible for medical decisions, diagnoses, and referrals to other providers (e.g. cardiologist) if indicated.
- 9.3.** Describe other resources available to conduct the research: Walgreens store #6587 fills approximately 750 prescriptions per day. The store is located in a densely populated part of Albuquerque, NM in high business/traffic areas. The goal of 50 patients during recruitment is a feasible goal which can be met. The facilities to conduct the research will be in an already established Walgreens Pharmacy that has individual/private space available for education implementation with each participant over the phone.

10. Prior Approvals

- 10.1** DNP project chair from MSU has approved project proposal, and [name] supervisor has approved the project.
- 10.2** Upload the required Departmental Review Form signed by your Department Chair (or authorized designee if the PI is the Department Chair) into Click under "supporting documents."
- 10.3** N/A; no radiation will be involved in this study.
- 10.4** N/A: no biological specimens will be involved in this study.

11 Multi-Site Research

- 11.1** This site will occur as a collaboration between the UNM College of Pharmacy, Walgreens Pharmacy, and a Doctor of Nursing (DNP) student enrolled in the DNP program at Missouri State University (MSU). All research procedures will occur at Walgreens pharmacy.
 - All sites will maintain the most current version of the protocol, consent document, and HIPAA authorization.

PROTOCOL TITLE: Evaluating the Effect of an Evidence-Based One Page with
Supplemental Visual Aids on the Knowledge and Perceptions of Blood Pressure
Management Among Adults with Hypertension

- All approved IRB protocols will be maintained at each site.
- All modifications will be communicated to sites, and approved (including approval by the site's IRB of record) before the modification is implemented.
- All engaged participating sites will safeguard data as required by local information security policies. Data will be stored in a locked filing cabinet at Walgreens Pharmacy Store #6587. The filing cabinet will be locked inside the pharmacy which is secured by an alarm system, and only accessible with those who have the authorized keys/codes. Data will be entered from paper copies and stored on UNM RedCap. Data will be analyzed at UNM. No data will be sent to MSU, other than in final summary form.
- All local site investigators will conduct the study appropriately.
- All non-compliance with the study protocol or applicable requirements will be reported in accordance with local policy.

11.2 The method to communicate: adverse events, problems, interim results, data/safety monitoring reports, and closure of the study will occur through UNM Redcap.

11.3 N/A; this is not an FDA-regulated trial.

12 Study Procedures

12.1 This study will occur at Walgreens Store #6587 in Albuquerque, NM. Recruitment will occur during standard-of-care follow up phone calls at Walgreens Pharmacy. If a patient would like to participate, the information will be mailed to them with a follow-up phone call to review all the information over the phone with them. Phone calls will be made in a private room in the pharmacy. [name], PharmD will oversee the study procedures at Walgreens Walgreens Store #6587.

12.2 Patients will be screened for eligibility for the study at Walgreens Store #6587, with pharmacists supervising the PharmD students. Screening will be conducted with the Interview Guide included in this IRB submission as "UNM HTN Prescreen for Potential Participants." Eligible potential participants will have consent forms read and given the opportunity to ask questions about the study. Participants may choose to enroll in the study at that time, or given more time to be mailed consent forms at home and decide at another time. Once the participant consents to participation, the materials will be mailed to the participant, and the participant will complete a pre-survey ("Pre-survey for UNM HTN Study") and pre-test ("Pre-test for UNM HTN Study") on blood pressure management. Participants will be provided a one-page education with supplemental visual aids on blood pressure management with education provided by PharmD students ("My Planned Behavior for Managing My Blood Pressure"). Participants will be provided a list of suggested apps and websites ("Evidence-

PROTOCOL TITLE: Evaluating the Effect of an Evidence-Based One Page with
Supplemental Visual Aids on the Knowledge and Perceptions of Blood Pressure
Management Among Adults with Hypertension

based Websites and Apps for Blood Pressure Management") that they may use if they have a smartphone and/or internet access.

After an initial teaching phone call performed by a PharmD student, a follow-up phone call will be conducted at week 4 and 8 of the participant's enrollment.

During each phone call, study personnel will use a telephone script titled "Phone Call Script for My Planned Behavior for Managing My Blood Pressure Participants" to discuss blood pressure goals, behavioral changes, and principles of blood pressure management.

At week 8, participants will either answer their questions over the phone or be reminded to complete a post-test ("Post-test for UNM HTN Study") and post-survey ("Post-survey for UNM HTN Study") and mail in using their SASE.

12.3 The information will be collected prospectively and information will be collected at the onset of enrollment, during an initial teaching phone call, during phone calls at week 4, and 8, and from mailed in pre/post-test; pre/post surveys.

12.4 Initial study activities will occur from the Walgreens Store #6587 in Albuquerque, NM by phone calls: recruitment, enrollment, and initial education. The rest of the information will be gathered by follow-up phone calls at 4 and 8 week intervals, and mail-outs. The phone calls will be made from the Walgreens Pharmacy clinic in a room where the investigator has privacy for the phone calls to speak with the participant.

12.5 Describe, in chronological order, all research procedures and interventions being performed and when they are performed. Include:

- Recruitment: Walgreens Store #6587 by phone
- Screening interview: Walgreens Store #6587 by phone
- Verbal consent and enrollment: Walgreens Store #6587 by phone
- One-page educational intervention ("My Planned Behavior for Managing My Blood Pressure (One Page Handout)") with supplemental visual aids ("DASH diet," "AHA Healthy for Good," and "AHA Blood Pressure Management") will be sent to the mailing address given by the participant with a self-addressed stamp envelope in order to return pre/post-test and pre/post-survey.
- One-page educational intervention with supplemental visual aids: from Walgreens Store #6587 via mail. Education on blood pressure management will be provided to the participant by PharmD students via a phone call after enrollment once patient receives items in the mail. ("Phone call Script for My Planned Behavior for Managing My Blood Pressure Participants").
- Follow-up phone calls at 4 and 8 week intervals: Phone calls will be made to the phone number provided by the participant. Phone calls will be made from private rooms at Walgreens Store #6587. Study personnel will use a phone script ("Phone call Script for My Planned Behavior for Managing My Blood

PROTOCOL TITLE: Evaluating the Effect of an Evidence-Based One Page with Supplemental Visual Aids on the Knowledge and Perceptions of Blood Pressure Management Among Adults with Hypertension

Pressure Participants") to discuss blood pressure goals, behavioral changes, and principles of blood pressure management.

- Post-test on blood pressure management ("Post-test for UNM HTN Study"): Walgreens Store #6587. The purpose of this test is to determine the participant's knowledge of blood pressure management after the educational intervention. The patient may return the completed test by mail, or answer the questions over the phone if they are unable to mail their responses.
- Post-survey ("Post-survey for UNM HTN Study"): Walgreens Store #6587. The purpose of this survey is to gauge the participant's perspectives on engaging in behavioral changes after the educational intervention. The patient may return the completed test by mail, or answer the questions over the phone if they are unable to mail their responses.

13 Data Analysis

- 13.1 Descriptive statistics will be used with demographic information, and paired t-tests will be used for the pre/posttest and pre/post surveys. The UNM Statistics Department will assist with statistical analysis.
- 13.2 Power analysis completed for the paired t-tests to detect difference in pre/post tests and surveys using: one tail, moderate effect size of 0.5, alpha probability of error of 0.05, and power standard of .95 resulted in n=45 (GPower, 2019).

14 Provisions to Monitor the Data to Ensure the Safety of Subjects

N/A. This study poses minimal risk to the patient as it utilizes only non-invasive screening interventions (education; surveys; follow-up phone calls).

15 Withdrawal of Subjects

- 15.1 A patient may be withdrawn from the study should they no longer meet inclusion criteria (for example, if they become pregnant during the study). The patient may also be withdrawn if they are not following the study protocol as agreed upon at the onset of the study. Should the patient no longer be able to be contacted after three phone call attempts, they will be withdrawn from the study. Data obtained up to that point of no contact will be maintained, and used for the study analysis.
- 15.2 The completion of this study will be on the final call to gather data & final post-test and post-survey from the participant. If the patient did make a behavior change of taking blood pressure at home, we will inquire at this time. Upon completion of the study, the participant will be encouraged to continue to see their primary care physician or other medical provider for continued blood pressure management.

PROTOCOL TITLE: Evaluating the Effect of an Evidence-Based One Page with
Supplemental Visual Aids on the Knowledge and Perceptions of Blood Pressure
Management Among Adults with Hypertension

15.3 This is an education-only intervention, and the patient may choose to immediately withdraw from the study and decline any further education or follow up phone calls. Should the patient choose to withdraw at any time, they will be encouraged to follow-up with their primary care physician or other medical provider for continued blood pressure management. Should the patient no longer be able to be contacted after three phone call attempts, they will be withdrawn from the study. Data obtained up to that point of no contact will be maintained, and used for the study analysis. Should there be unexpected circumstances such as pregnancy or hospitalization for a major cardiac event (stroke, myocardial infarction, or heart failure exacerbation), that participant's data will be used up to the time of the event that causes withdraw.

15.4 Collected data for any withdrawn participants will be maintained in accordance with study protocol.

15.5 Participants will be informed in the consent process that they may choose to withdraw from the study at any time for any reason.

16 Data Management/Confidentiality

16.1 N/A Data will be entered and stored on UNM Redcap.

16.2 The research team will have access to stored information about the subjects that will be maintained in a locked filing cabinet inside a pharmacy that is accessible only with keys and/or personal access codes. The research team will have access to the UNM Redcap Database.

16.3 This research will involve the collection of patient's name. The patient's name is needed for review of their medication profile at Walgreens and for making follow-up phone calls. Participants will be assigned an ID code to be placed on all documents. The ID code and the participant's name will not be recorded on the same documents. The only link between ID code and participants' names will be on a master list which will be stored in a locked filing cabinet which will be placed inside a pharmacy accessible only via personal access codes and keys. Information contained on envelopes that patients may mail back to the pharmacy (patient name and address) will be shredded upon receipt.

16.4 This research will involve access to Protected Health Information (PHI), including the patient's medication profile at Walgreens.

16.5 The data is not publicly available.

16.6 The data is not considered sensitive; information collected in this study will relate only to the patient's blood pressure management and their behavior and behavioral changes to manage their blood pressure.

16.7 This study will not utilize a Certificate of Confidentiality.

PROTOCOL TITLE: Evaluating the Effect of an Evidence-Based One Page with
Supplemental Visual Aids on the Knowledge and Perceptions of Blood Pressure
Management Among Adults with Hypertension

16.8 Data will be stored in locked filing cabinet inside a pharmacy that is only accessible with keys and/or personal access codes. Data will be entered into UNM Redcap.

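### No visible step places the pre-test and pre-survey before the mailed handouts, so some baselines may be taken after exposure, and the post-test may be held for up to about 8 weeks

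*Combined protocol and SAP*

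**What the plan says.** All references are to the combined protocol and SAP.

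- **3.1** describes "human participants assigned to an intervention of a one-page handout with supplemental visual aids and optional use of suggested apps and websites". The printed handouts are therefore part of the intervention, not just an accompaniment to it.
- **1.2** frames the hypothesis as improvement "after receiving education from PharmD students using a one-page teaching protocol with supplemental visual aids", so the student calls are part of the intervention too.
- **6.1** itemises the initial mailing as follows: "one-page with supplemental handouts/visual aids, list of suggested apps and web sites, pre/post survey and pre/post-test with self-addressed stamped envelopes (SASE", plus a pill box.
- **12.2** reads: "Once the participant consents to participation, the materials will be mailed to the participant, and the participant will complete a pre-survey" and a pre-test. It next mentions the one-page education by students, then the teaching call. On follow-up: "a follow-up phone call will be conducted at week 4 and 8 of the participant's enrollment". On the final instruments: "At week 8, participants will either answer their questions over the phone or be reminded to complete a post-test" and post-survey.
- **12.3** names the onset of enrolment as a collection point, ahead of the teaching call.
- **12.5** answers the template prompt "Describe, in chronological order, all research procedures and interventions being performed and when they are performed". It goes from verbal consent to mailing the handouts with a return envelope for the pre- and post-instruments. The teaching call follows once the items have arrived. The post-test and post-survey have their own entries; the pre-test and pre-survey have none.
- **7.1** gives the primary endpoint as "change in participant's knowledge of blood pressure management; change in participant's perception of making lifestyle changes to manage their hypertension". **13.1** analyses both instruments by paired t-test.

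**The concern.** No control group is described, so the within-person change is the only contrast for both primary endpoints. It measures the effect of the intervention only if the first score is taken before exposure. Here the handouts travel at the same stage as the baseline forms, and the teaching call waits for receipt of the items, not for a completed baseline. A participant who follows the plan as written could read the handouts, complete the pre-test, and then take the call.

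Two effects are possible, in opposite directions. A baseline taken after reading already contains some of the gain, so the measured change shrinks and power is lost. Post-test forms that arrive at the start can be looked at during the weeks of education, which could raise the final knowledge score. If the pre- and post-test items are the same (the forms are not available here), the pre-test already reveals them and holding the post-test adds less.

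**Working it through.** **1. Order of steps, set side by side**

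| Step | 6.1 | 12.2 / 12.3 | 12.5 |
|---|---|---|---|
| Handouts mailed | start of study | after consent | after verbal consent |
| Pre-test, pre-survey | mailed at start of study | after the mailing; mentioned before the education | no entry |
| Teaching call | not stated | after the pre-instruments in order of mention | once the items have arrived |
| Post-test, post-survey | mailed at start of study | week 8, by phone or by reminder to mail in | own entries, mail or phone |

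The order in 12.2 and 12.3 supports a baseline before the call. No column puts the baseline before the handouts.

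**2. Time the post-test is held.** Week 8 is counted from enrolment: 8 × 7 = 56 days. With an assumed 3-7 days for the mail, forms are in hand for 56 − 7 = 49 to 56 − 3 = 53 days, hence up to about 8 weeks. This applies only to those who do not return them earlier.

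**3. The plan's sample size.** Inputs from 13.2: one tail, alpha 0.05, effect 0.5 SD of the change, n=45. Power = P(T > t₀.₉₅,₄₄), where T is noncentral t with 44 df and noncentrality 0.5 × √45 = 3.354. The critical value is 1.680 and power is 0.951. The stated n=45 at 95% power reproduces; there is no arithmetic error.

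**4. Illustration of a contaminated baseline.** Let *a* be the share of the eventual gain already present at the pre-test. This is an assumption; the documents give no value. The observed effect is 0.5 × (1 − *a*), with the SD of the change held fixed.

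| *a* (assumed) | Effect (SD) | Noncentrality, n=45 | Power, n=45 | Power, n=50 |
|---|---|---|---|---|
| 0 | 0.50 | 3.354 | 0.951 | 0.967 |
| 10% | 0.45 | 3.019 | 0.908 | 0.932 |
| 20% | 0.40 | 2.683 | 0.841 | 0.874 |
| 30% | 0.35 | 2.348 | 0.748 | 0.787 |

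To see what *a* implies, write *a* = *p* × *h*, with *p* the share of participants who read the handouts first and *h* the share of the gain that the handouts give without the calls. Half reading first and handouts giving 40% of the gain means *a* = 0.5 × 0.4 = 20%. Such a mixture also adds spread: the SD becomes √(1 + 0.5 × 0.5 × (0.5 × 0.4)²) = √1.01 = 1.005, and power is 0.837 instead of 0.841.

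**5. Inflation from seeing the post-test early.** Not quantified: the items are not available, and no input in the documents bears on it.

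**The case against.** The case on the other side is substantial.

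- *The intended order is clear enough.* 12.2 mentions the pre-instruments before the education, and 12.3 lists enrolment before the teaching call. This stands for the call. It does not reach the printed handouts, which are available to read before the call.
- *An instruction may already exist.* The forms and phone script were submitted separately. A direction to complete the baseline before reading would answer much of the point, so the finding is conditional on those forms. Compliance would still be hard to verify, although the teaching call could ask whether the handouts had been read.
- *Early reading is conservative.* Correct. It exposes the participant to only part of the intervention and works against finding an effect.
- *The sizes are assumed.* Also correct; the table is illustrative.

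Stronger readings that a reader might infer are not supported. That everything arrives in a single envelope is natural but remains an inference: 6.1 says only that the items are mailed at the start. That baselines will be post-exposure does not follow, because the text permits this order without requiring it. That both changes must be biased toward zero is an assumption for the perception survey, since nothing shows that the handouts alone move perceptions the same way as the full programme. That a positive result would be spurious does not follow from early reading.

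**Conclusion.** The point holds as a gap in procedure. The plan visibly places the baseline before the teaching call but not before the handouts, and 12.5 omits the baseline step altogether. Unless the separate forms set an order, some baselines may be contaminated, in the only contrast available for both primary endpoints.

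The likely direction is a smaller measured change, assumed for perception, with an opposing effect of unknown size from holding the post-test. The net direction is therefore unknown. It would be wrong to conclude that the trial is underpowered: the planned power of 0.951 is correct, and the losses above rest wholly on an assumed *a*. The reason to act is that the order is cheap to set beforehand and can be reconstructed afterwards only by asking participants. Severity: should-fix.

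**What to change.** In 6.1, 12.2 and 12.5:

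1. Obtain the pre-test and pre-survey on the enrolment call, straight after verbal consent and before the handouts are mailed. Add this as a step in 12.5 between consent and the mailing. For those who take longer to decide, use the call on which they consent.
2. Take the post-test and post-survey out of the first mailing and collect them by phone at the week-8 call, which 12.2 already allows. 12.5 offers the phone only to those unable to mail, so its wording needs aligning.
3. If post-instruments are mailed instead, send them shortly before week 8. Posted at week 8 itself, the last returns would run late: enrolment on 30 September puts week 8 at 25 November. With an assumed 3-7 days each way, forms arrive 28 November-2 December and return 1-9 December, before any time to complete them, inside the planned December analysis.
4. Record the date and mode of each instrument. Keep everyone with both scores in the primary analysis, and use the dates only to describe departures from the order.

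**Cost.** No added participants or visits; the pre-instruments are already a participant task. At an assumed 5-15 minutes each time, the baseline takes 50 × 5/60 = 4.2 to 50 × 15/60 = 12.5 staff hours. Both occasions by phone take 100 × 5/60 = 8.3 to 100 × 15/60 = 25 hours. Phone answers to the perception survey may be more favourable; using a caller other than the teaching student limits this. Answering the post-test with the handouts to hand is a separate risk that this change does not remove.
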